7.3.4. Concomitant therapy for ulcerative colitis

7.3.4.1. Drug therapy

The record of treatments• for ulcerative colitis used from the date of commencement of XELJANZ treatment to the date of completion of the observation period (or date of XELJANZ discontinuation) should include the following information.

- 1. Drug name
- 2. Route of administration
- 3. Dosage form (topical agents only)
- 4. Duration of treatment
 - *: 5-ASAs (oral, enema, suppository), steroids (oral, enema, suppository, injection), immunomodulators (oral, injection), biological products (injection)

7.3.4.2.Non-drug therapy

The record of non-drug treatments given from the date of commencement of XELJANZ treatment to the date of completion of the observation period (or date of XELJANZ discontinuation) should include the following information.

- 1. Name of the therapy
- 2. Period of administration
- 3. Reason for the administration of non-drug therapy

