2.1. Study Design

This is a multicenter cohort investigation to be conducted in patients with ulcerative colitis treated with XELJANZ in clinical settings.

• Registration criteria

Patients must meet all of the following inclusion criteria to be eligible for inclusion in the study:

- •Patients with ulcerative colitis treated with XELJANZ
- •Patients naive to XELJANZ in the treatment of ulcerative colitis
- Sample size

470 to be collected in the safety analysis set (495 to be registered*)

• Rationale

Based on the results of clinical studies conducted up to approval, the incidence of herpes zoster in Japanese patients with ulcerative colitis chronically treated with XELJANZ was higher than that in the overall population of the studies. Therefore, on the assumption that the true incidence of herpes zoster in Japanese patients with ulcerative colitis is 8/100 person-years, the sample size will be 470 when the probability of the lower limit of 95% confidence interval for the incidence of herpes zoster not falling below 4/100 person-years (results for the overall population of the studies) is 80%.

- *: If it is assumed that 5% of the registered patients are unevaluable for the safety due to failure to show up or other reasons, 495 patients need to be registered to ensure that 470 patients are included in the safety analysis set.
- Safety specification

Important Identified Risks

- Serious infections (including tuberculosis, pneumonia, pneumocystis pneumonia, sepsis, opportunistic infection)
 - Herpes zoster
 - Neutropenia, lymphopenia, oligochromemia
 - Hepatic impairment
 - Reactivation of hepatitis B virus
 - Gastrointestinal perforation
 - Interstitial lung disease
 - Venous thrombosis
 - Malignant tumor
 - Cardiovascular event

Important Potential Risks

• Rhabdomyolysis, myopathy

Important Missing Information

Not applicable.

• Observation period

Each patient will be observed for 60 weeks from the start day of the treatment with this drug. Patients treated with this drug for more than 60 weeks will, however, be observed to the end of this study (June 2021). For patients who discontinued the treatment with this drug, data will be collected until the discontinuation.

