All adverse events (AEs) occurring from the start of treatment to the end of the observation period will be collected for patients whose observation period is 60 weeks or less. For patients whose observation period exceeds 60 weeks, all AEs will be collected until 60 weeks and thereafter only malignancies and AEs leading to discontinuation of treatment will be collected.

• Analysis for safety evaluation

In the safety analysis set, the onset of major adverse reactions (AEs considered by the physician to be related to this drug), incidence of adverse reactions (number/percentage of patients with adverse reactions), and incidence of adverse events per duration of exposure (100 × number of patients with adverse reactions / total duration of exposure / 100 person-years) will be set as primary analysis items. In addition, factors that may affect the onset of adverse reactions will also be examined by conducting subgroup analyses based on patient background and other factors.

• Analysis for effectiveness evaluation

In the effectiveness analysis set, the rate of remission based on partial Mayo score will be set as primary analysis items.

• Dosage and administration of this drug

For induction, the recommended dose of this drug is 10 mg administered twice daily (10 mg BID [bis in die]) for 8 weeks. If the response is inadequate after the 8 weeks course of treatment, another 8 weeks course may be administered.

For maintenance, the recommended dose is 5 mg twice daily (5 mg BID). If the response decreases during the maintenance, the dose level may be increased to 10 mg BID. Intractable patients for whom prior drug therapies (e.g., a TNF inhibitor) were ineffective may be treated with 10 mg BID.

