Using the SAS and EAS, a breakdown of patients by each of the following factors will be presented in terms of n and proportion. Concomitant medications and non-drug therapies will be defined in align with the data collection period for adverse reactions and AEs so that relationship to adverse reactions and AEs can be assessed.

- Concomitant medications (drugs recorded in the CRF entry "Drug therapies for UC prior treatment and concomitant therapies" that were used in the period from the start of the treatment with this drug to the discontinuation of treatment or 60 weeks after the start of treatment, whichever came first)
- Non-drug therapies (non-drug therapies recorded in the CRF entry "Non-drug therapies for UC prior treatment and concomitant therapies" that were used in the period from the start of the treatment with this drug to the discontinuation of treatment or 60 weeks after the start of treatment, whichever came first)
- Prior medications (medications recorded in the CRF entry "Past history of treatment for UC biological therapeutics", and medications recorded in the CRF entry "Drug therapies for UC prior treatment and concomitant therapies" of which administration had been started by the day before the start of the treatment with this drug)

• Dosing status of Xeljanz tablets

Using the SAS (including the subgroups by mean daily dose) and the set of patients treated for a long term (including the subgroups by mean daily dose), dosing data for this drug will be summarized with respect to the following aspects:

- Starting daily dose [5 mg, 10 mg, 15 mg, 20 mg, >20 mg]
- Duration of treatment [\leq 15 weeks, >15 to \leq 30 weeks, >30 to \leq 45 weeks, >45 to \leq 60 weeks, >60 to \leq 75 weeks, >75 to \leq 90 weeks, >90 to \leq 105 weeks, >105 to \leq 120 weeks, >120 to \leq 135 weeks, >135 weeks]
- Total duration of treatment (patient-years) [≤15 weeks, >15 to ≤30 weeks, >30 to ≤45 weeks, >45 to ≤60 weeks, >60 to ≤75 weeks, >75 to ≤90 weeks, >90 to ≤105 weeks, >105 to ≤120 weeks, >120 to ≤135 weeks, >135 weeks] (The total duration of treatment in each category and the accumulated total duration of treatment will be presented.)
- Mean daily dose by duration of treatment (mg) (summary statistics) [<15 mg, ≥15 mg] [<17 mg,
 ≥17 mg], with the following categories for the duration of treatment:
 - Any duration of treatment
 - Duration of treatment ≤15 weeks
 - Duration of treatment > 15 to ≤ 30 weeks
 - Duration of treatment >30 to <45 weeks

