8.2.3. Safety analyses

Adverse reactions or AEs included in a summarization will be those that developed from the start of treatment to the end of the observation period or 60 weeks after the start of treatment, whichever came first, except for malignancy, for which all events occurring by the end of observation period will be included in a summarization. All adverse reactions and AEs reported in this study will be included in a listing.

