- Malignancy
- Cardiovascular events (including lipids increased and hyperlipidaemia)
- Cardiovascular events (excluding lipids increased and hyperlipidaemia)
- Lipids increased and hyperlipidaemia
- Rhabdomyolysis and myopathy

In addition, patients who experienced adverse reactions in the scope of the safety specification will be summarized in terms of n and proportion by SOC and PT, for different kinds of action taken and outcome.

Timing of onset of elements in the safety specification

Patients who experienced adverse reactions of each element in the safety specification will be summarized by timing of first onset, in terms of n and proportion as well as incidence and its 95% CI. For the purpose of summarization by time to onset, the denominator to calculate the proportion will be the number of patients who took at least one dose during each time category, and the denominator to calculate the incidence will be the duration of exposure in each time category. The categories for onset timing will be given by $[\le 15 \text{ weeks}, > 15 \text{ to} \le 30 \text{ weeks}, > 30 \text{ to} \le 45 \text{ weeks}, > 45 \text{ to} \le 60 \text{ weeks}]$, except for malignancy, for which given by ≤ 15 weeks, ≥ 15 to ≤ 30 weeks, ≥ 30 to ≤ 45 weeks, ≥ 45 to ≤ 60 weeks, ≥ 60 to ≤ 75 weeks, >75 to ≤ 90 weeks, >90 to ≤ 105 weeks, >105 to ≤ 120 weeks, >120 to ≤ 135 weeks, >135 weeks].

Relationship between concomitant drugs and adverse reactions

To investigate the relationship between concomitant biologics/immunosuppressants or concomitant CYP3A4 inhibitors/CYP2C19 inhibitors and adverse reactions included in the scope of the safety specification, development of those adverse reactions will be summarized in patients with and without concomitant use of a biologic/immunosuppressant and in patients with and without concomitant use of a CYP3A4 inhibitor/CYP2C19 inhibitor, by PT in terms of number of patients. Concomitant drugs used after the first onset of a target event will be excluded from the summarization. Concomitant drugs considered in this investigation include:

- Biologics (including recombinants)/immunosuppressants: abatacept, adalimumab, anakinra, azathioprine, baminercept, canakinumab, certolizumab, certolizumab pegol, cyclosporine, efalizumab, etanercept, golimumab, infliximab, ofatumumab, rituximab, Syk kinase inhibitors, tacrolimus hydrate, tocilizumab, sarilumab, zanolimumab, vedolizumab, ustekinumab, secukinumab, ixekizumab, and 6-mercaptopurine

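### Concomitant-drug use is assessed only to Week 60 while malignancy is counted to the end of observation, so some late malignancies would be tabulated as 'without' a drug whose use was never assessed

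*SAP*

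**What the plan says.** **Exposure window.** SAP 8.2.2 says that "Concomitant medications and non-drug therapies will be defined in align with the data collection period for adverse reactions and AEs", and gives the purpose: "so that relationship to adverse reactions and AEs can be assessed". The window for each drug then runs from the start of XELJANZ "to the discontinuation of treatment or 60 weeks after the start of treatment, whichever came first". No exception is made for malignancy.

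**Outcome window.** SAP 2.1 says of patients observed beyond Week 60 that "all AEs will be collected until 60 weeks and thereafter only malignancies and AEs leading to discontinuation of treatment will be collected". SAP 8.2.3 limits summaries to the first 60 weeks, "except for malignancy, for which all events occurring by the end of observation period will be included in a summarization". SAP 6.1 (endpoints), 8.1.4 (person-years) and 8.1.5 (Kaplan-Meier) make the same exception. For a patient still on treatment, observation ends in June 2021; otherwise it ends at discontinuation.

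**Where the two meet.** SAP 8.2.3.1 (adverse reactions) and 8.2.3.2 (adverse events) count safety-specification events, by preferred term, in patients with and without a concomitant biologic/immunosuppressant and with and without a CYP3A4/CYP2C19 inhibitor. Malignancy belongs to that specification, and SAP 2.1 lists it as an important identified risk. The only timing rule in these tables is "Concomitant drugs used after the first onset of a target event will be excluded from the summarization".

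**What is collected.** Protocol 7.3.4.1 asks for drugs for ulcerative colitis (UC) up to completion of the observation period or discontinuation. It lacks the sentence on patients treated for more than 60 weeks that appears in Protocol 7.3.3, 7.3.9 and 7.3.11.

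**The concern.** The windows agree for every safety-specification element except malignancy, so the alignment that SAP 8.2.2 claims fails for that one. After Week 60 the plan goes on looking for malignancies but stops looking at co-medication. Nothing in 8.2.3.1 or 8.2.3.2 brings back a drug started between Week 60 and onset, and no category stands for exposure not assessed. Such a case therefore falls into 'without' by default.

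The risk-factor list in SAP 6.4 and the subgroups in 5.4.2 cover treatment before XELJANZ. The with/without split is the plan's only tabulation of co-exposure during treatment. Malignancies will be few, so one case in the wrong column can change what a reader takes from the table.

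**Working it through.** The plan states no figure on this point, so there is none to reproduce. The check compares the two windows and measures the gap.

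**1. Windows side by side**

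| Item | Ends at | Source |
|---|---|---|
| Concomitant drug, any | discontinuation or Week 60, whichever is first | SAP 8.2.2 |
| Events other than malignancy | end of observation or Week 60, whichever is first | SAP 6.1, 8.1.4, 8.1.5, 8.2.3 |
| Malignancy | end of observation, no cap | SAP 6.1, 8.1.4, 8.1.5, 8.2.3 |

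Adverse events leading to discontinuation are also collected after Week 60, but SAP 8.2.3 keeps them out of the summaries. Malignancy is the only element affected.

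**2. Who is affected.** All of these must hold: still on XELJANZ after Week 60; malignancy with onset after Week 60; no listed drug used from treatment start to Week 60; first listed drug begun after Week 60 and before onset. Suppose a malignancy occurs at Week 100. With azathioprine first begun at Week 70 the case is counted 'without'. With azathioprine begun at Week 40 it is counted 'with', because SAP 8.2.2 takes any use inside the window.

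**3. Length of the gap.** Inputs: investigation period May 2018 to June 2021 (Protocol 7.2.3), cut-off taken as 30 June 2021, and a patient who stays on treatment. Weeks of follow-up W = days / 7; gap = W − 60.

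| Start | Days | W | Gap (weeks) | Gap / W |
|---|---|---|---|---|
| 25 May 2018 | 1132 | 161.7 | 101.7 | 63% |
| 1 January 2019 | 911 | 130.1 | 70.1 | 54% |
| 17 December 2019 | 561 | 80.1 | 20.1 | 25% |
| 6 May 2020 | 420 | 60.0 | 0 | 0% |

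Without any assumption on dates, six of the ten malignancy onset categories in SAP 8.2.3.1 (>60 to ≤75 weeks up to >135 weeks) lie beyond Week 60.

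**4. Share of malignancy follow-up without coverage (illustration).** Share = 1 − E[min(T, 60)] / E[T], with T the weeks on observation. Assumed, not in the documents: entry uniform from 25 May 2018 to the end of December 2019, and a constant discontinuation rate.

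| Still treated at Week 60 | Share after Week 60 | Late person-years, 470 patients |
|---|---|---|
| 100% | 50% | 540 |
| 70% | 41% | 310 |
| 50% | 32% | 187 |
| 35% | 25% | 111 |

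Moving the assumed end of entry between May 2019 and June 2020 widens the range of the share to 21–56%.

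**5. From coverage gap to misplaced cases (illustration).** Misplaced cases = late person-years × malignancy rate × share of patients who first start a listed drug after Week 60 and before onset. The documents give neither of the last two. Assuming 0.5 to 2 malignancies per 100 person-years and 2% to 10% first starts:

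- low: 111 × 0.005 × 0.02 = 0.01
- high: 310 × 0.02 × 0.10 = 0.6
- high with no discontinuation: 540 × 0.02 × 0.10 = 1.1

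On these assumptions the expected number lies between almost none and about one.

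**The case against.** **The window may not govern these tables.** SAP 8.2.3.1 and 8.2.3.2 do not restate the 60-week limit and carry their own timing rule. The revision history also shows that the drug definition for the relationship analysis and the drug description in 8.2.2 were edited in different SAP versions. This stands as a caution. But the current text gives no other definition, and 8.2.2 says its window exists so that drug–event relationships can be assessed.

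**Drug records may simply stop at Week 60.** Protocol 7.2.5 sets a 60-week observation period, but Table 1 calls Booklet 3 (Week 61 onward) an observation period too, and SAP 2.1 has such patients observed to June 2021. The schedule table is too damaged in the available text to settle whether UC drugs were recorded later, and the case report form is not supplied. If they were not recorded, the cap reflects the data available. Even then, 'without' is the wrong label for exposure nobody assessed.

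**Late malignancies remain visible.** SAP 8.2.3 and section 9 list all reported events. That is true, but the listings do not correct the tables, and no co-medication column is specified.

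**Three stronger readings a reader might infer.** None is supported.

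- *Every late malignancy with a drug begun after Week 60 is misplaced.* Use of any listed drug by Week 60 keeps the case in 'with'.
- *Up to 63% of malignancies are misclassified.* That figure is uncovered follow-up for an early starter who stays on treatment.
- *The table understates a link between combined immunosuppression and malignancy.* The tables give numbers of patients by preferred term, with no rate, ratio, interval or test. Patients without malignancy who start a drug after Week 60 are capped in the same way. Only the case counts can be said to shift, from 'with' to 'without'.

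**Conclusion.** The point holds in a limited form. The alignment claimed in SAP 8.2.2 is untrue for malignancy, and the rule as written labels unassessed exposure as 'without' for an important identified risk. The uncovered stretch is long: about 102 weeks for a patient starting in late May 2018, none for starts from about 6 May 2020. The number of cases in the wrong column is probably very small and cannot be derived from the documents; the range in step 5 rests wholly on assumed rates. The effect is on descriptive case counts.

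The conclusion rests on reading the 8.2.2 window into 8.2.3.1 and 8.2.3.2. It does not depend on whether later drug records exist: if they do, the SAP leaves them out; if they do not, 'without' means unknown. The correction is cheap and worth making, but it does not threaten the study's main safety results.

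**What to change.** 1. In the malignancy rows of the concomitant-drug tables in SAP 8.2.3.1 and 8.2.3.2, count only malignancies with onset within 60 weeks, so that outcome and exposure windows match as they do for the other elements.
2. Show later malignancies in a separate row or listing, with the listed drugs known up to Week 60 and later co-medication marked 'not assessed' instead of 'without'.
3. Amend the alignment statement in SAP 8.2.2 to except malignancy, and state in 8.2.3.1 and 8.2.3.2 which window applies.
4. If UC drug records after Week 60 exist, add pre-onset co-medication for the late cases to that listing. Do not define exposure up to onset for cases and up to end of observation for non-cases: non-cases would have longer to become 'with', and the unequal windows would add bias of their own.

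Cost: SAP wording, one filter and one label in two sets of tables, and no new data collection. The downside is that the few late malignancies leave the main with/without split. Within the first 60 weeks, cases are still cut at onset and non-cases at Week 60 or discontinuation; that is common to all elements and is not changed here.

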8.2.3. Safety analyses

Adverse reactions or AEs included in a summarization will be those that developed from the start of treatment to the end of the observation period or 60 weeks after the start of treatment, whichever came first, except for malignancy, for which all events occurring by the end of observation period will be included in a summarization. All adverse reactions and AEs reported in this study will be included in a listing.

8.2.3.1. Adverse reactions

• All adverse reactions

Adverse reactions will be summarized by SOC and PT in terms of number and proportion of patients.

Serious adverse reactions

Serious adverse reactions will be summarized by SOC and PT in terms of number and proportion of patients.

• Details of adverse reactions

Adverse reactions in different categories defined with respect to the following factors will be summarized by SOC and PT in terms of number and proportion of patients. For the factor time to onset, the number of patients who took at least one dose during each time category will be used as the denominator to calculate the proportion.

- Seriousness [serious, non-serious]
- Known/unknown [known, unknown]
- Time to onset [≤15 weeks, >15 to ≤30 weeks, >30 to ≤45 weeks, >45 to ≤60 weeks, >60 to ≤75 weeks, >75 to ≤90 weeks, >90 to ≤105 weeks, >105 to ≤120 weeks, >120 to ≤135 weeks, >135 weeks]
- Action taken [permanent discontinuation of treatment, temporary discontinuation or dose reduction, dose increase, no change]
- Outcome [not recovered, resolved/recovered, recovered with sequelae, improved, death, unknown]

Patients who experienced multiple adverse reactions of the same adverse reaction (identical PT) will be summarized as follows:

- For seriousness: Patients who experienced both serious and non-serious adverse reactions of the same PT will be handled as having experienced a serious event.
- For known/unknown: Priority will be given to "unknown" if both experienced.
- For time to onset: The day to the first onset will be used.
- For action taken: If multiple actions were taken, only one kind of action will be adopted with the order of priority being permanent discontinuation, temporary discontinuation/dose reduction, and other (no change or dose increase).
- For outcome: The outcome for the last event will be used.

Safety specification

The following adverse reactions included in the scope of the safety specification will be summarized in terms of number and proportion of patients, as well as incidence and its 95% CI.

- Serious infections (including tuberculosis, pneumonia, pneumocystis pneumonia, sepsis, and opportunistic infection)
- Herpes zoster
- Neutrophils decreased, lymphocytes decreased, haemoglobin decreased
- Hepatic function disorder
- Hepatitis B virus reactivation (in patients with past history or complication of hepatitis B virus carrier)
- Gastrointestinal perforation
- Interstitial lung diseases
- Venous thromboembolism
- Malignancy
- Cardiovascular events (including lipids increased and hyperlipidaemia)
- Cardiovascular events (excluding lipids increased and hyperlipidaemia)
- Lipids increased and hyperlipidaemia
- Rhabdomyolysis and myopathy

In addition, patients who experienced adverse reactions in the scope of the safety specification will be summarized in terms of n and proportion by SOC and PT, for different kinds of action taken and outcome.

Timing of onset of elements in the safety specification

Patients who experienced adverse reactions of each element in the safety specification will be summarized by timing of first onset, in terms of n and proportion as well as incidence and its 95% CI. For the purpose of summarization by time to onset, the denominator to calculate the proportion will be the number of patients who took at least one dose during each time category, and the denominator to calculate the incidence will be the duration of exposure in each time category. The categories for onset timing will be given by $[\le 15 \text{ weeks}, > 15 \text{ to} \le 30 \text{ weeks}, > 30 \text{ to} \le 45 \text{ weeks}, > 45 \text{ to} \le 60 \text{ weeks}]$, except for malignancy, for which given by ≤ 15 weeks, ≥ 15 to ≤ 30 weeks, ≥ 30 to ≤ 45 weeks, ≥ 45 to ≤ 60 weeks, ≥ 60 to ≤ 75 weeks, >75 to ≤ 90 weeks, >90 to ≤ 105 weeks, >105 to ≤ 120 weeks, >120 to ≤ 135 weeks, >135 weeks].

Relationship between concomitant drugs and adverse reactions

To investigate the relationship between concomitant biologics/immunosuppressants or concomitant CYP3A4 inhibitors/CYP2C19 inhibitors and adverse reactions included in the scope of the safety specification, development of those adverse reactions will be summarized in patients with and without concomitant use of a biologic/immunosuppressant and in patients with and without concomitant use of a CYP3A4 inhibitor/CYP2C19 inhibitor, by PT in terms of number of patients. Concomitant drugs used after the first onset of a target event will be excluded from the summarization. Concomitant drugs considered in this investigation include:

- Biologics (including recombinants)/immunosuppressants: abatacept, adalimumab, anakinra, azathioprine, baminercept, canakinumab, certolizumab, certolizumab pegol, cyclosporine, efalizumab, etanercept, golimumab, infliximab, ofatumumab, rituximab, Syk kinase inhibitors, tacrolimus hydrate, tocilizumab, sarilumab, zanolimumab, vedolizumab, ustekinumab, secukinumab, ixekizumab, and 6-mercaptopurine
- CYP3A4 inhibitors/CYP2C19 inhibitors: clarithromycin, telithromycin, nefazodone, itraconazole, ketoconazole, atazanavir, darunavir, indinavir, lopinavir, nelfinavir, ritonavir, saquinavir, tipranavir, tacrolimus hydrate, cyclosporine, amitriptyline, clomipramine, fluconazole, fluvoxamine, imipramine, ticlopidine, esomeprazole, fluoxetine, moclobemide, omeprazole, and voriconazole

• Adverse reactions in patients excluded from and included in the SAS

Adverse reactions occurring in CRF-collected patients who are excluded from the SAS will be listed in tabular form. In addition, adverse reactions occurring in patients included in the SAS and in patients excluded from the SAS will be summarized by SOC and PT in terms of n and proportion of patients.

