7.4. Data sources

In this study, the investigators extract the necessary information using medical charts, medical records and other information in accordance with the protocol.

- 7.5. Study size
- 7.5.1. Planned sample size

470 to be collected in the safety analysis set (495 to be registered•)

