7.5.2. Rationale for sample size

Based on the results of clinical studies conducted up to approval, the incidence of herpes zoster in Japanese patients with ulcerative colitis chronically treated with XELJANZ was higher than that in the overall population of the studies. Therefore, on the assumption that the true incidence of herpes zoster in Japanese patients with ulcerative colitis is 8/100 person-years, the sample size will be 470 when the probability of the lower limit of 95% confidence interval for the incidence of herpes zoster not falling below 4/100 person-years (results for the overall population of the studies) is 80%.

*: If it is assumed that 5% of the registered patients are unevaluable for the safety due to failure to show up or other reasons, 495 patients need to be registered to ensure that 470 patients are included in the safety analysis set.

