8.1.4. Analyses based on the person-year method

The incidence of an event per exposure duration will, if it should be presented, be calculated using the following formula:

Incidence (patients/100 patient-year) = $100 \times y/PT$

y: Number of patients who experienced the event

PT: Total exposure duration (years),

Here the exposure duration for event-free patients will be given by the period from the start of treatment to the end of the observation period unless this exceeds 60 weeks; if this period exceeds 60 weeks, the exposure duration should be 60 weeks. The exposure duration for patients who experienced the event is, in principle, the period from the start of treatment to the day the event was first observed, but if the event occurred 60 weeks or later after the start of treatment, the patient will be handled as an event-free patient and their exposure duration should be 60 weeks. For malignancy, however, no such upper limit will be set; the exposure duration for malignancy-free patients will be the period from the start of treatment to the end of the observation period, while the exposure duration for patients in whom malignancy developed will be the period from the start of treatment to the day of the first observation of the event. The 95% CI will be calculated using the following formula:

$$\left[\frac{100}{PT} \times \frac{1}{2} \chi_{2y}^{2}(\alpha/2), \frac{100}{PT} \times \frac{1}{2} \chi_{2(y+1)}^{2}(1-\alpha/2)\right]$$

y: Number of observed events

 $\chi^2_{2\nu}(\alpha/2)$: The $\alpha/2$ -fractile point of the chi-square distribution with 2y degrees of freedom

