8.2.3.3. Subgroup analyses

Analyses by dosage subgroup

(1) Safety analysis of the treatment with 10 mg BID

To evaluate the safety of the treatment with this drug administered mainly at a dose of 10 mg BID, the following analyses will be performed in the patients treated mainly at 10 mg BID defined in Section 5.4.1 and results will be compared with those in the entire SAS. To eliminate the effect of including patients who discontinued treatment during the induction phase, similar analyses will also be performed in patients treated mainly at 10 mg BID for a long term and results will be compared with those in the patients treated for a long term defined in Section 5.4.1:

- Adverse reactions of each element in the safety specification will be summarized in terms of number and proportion of patients as well as incidence and its 95% CI.
- Adverse reactions will be summarized by SOC and PT in terms of number and proportion of patients.

In addition, to investigate the temporal change in the risk of occurrence of each event, the following analyses will be performed in the patients treated mainly at 10 mg BID and results will be compared with those in the SAS:

- Patients who experienced adverse reactions of each element in the safety specification will be summarized by timing of first onset, in terms of n and proportion as well as incidence and its 95% CI. For the purpose of summarization by time to onset, the denominator to calculate the proportion will be the number of patients who took at least one dose during each time category, and the denominator to calculate the incidence will be the duration of exposure in each time category. The categories for onset timing will be given by [\leq 15 weeks, >15 to \leq 30 weeks, >30 to \leq 45 weeks, >45 to \leq 60 weeks], except for malignancy, for which given by [\leq 15 weeks, >15 to \leq 30 weeks, >30 to \leq 45 weeks, >45 to \leq 60 weeks, >60 to \leq 75 weeks, >75 to \leq 90 weeks, >90 to \leq 105 weeks, >105 to \leq 120 weeks, >120 to \leq 135 weeks, >135 weeks].
- A Kaplan-Meier plot will be presented for the time to first onset of each element in the safety specification.
- (2) Evaluation of dose response of the safety

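### By-band first-onset proportions keep patients who have already had the event in the denominator, which can distort the apparent time trend and the dose-group comparison

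*SAP*

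**What the plan says.** In SAP 8.2.3.1, patients with each element of the safety specification are "summarized by timing of first onset, in terms of n and proportion as well as incidence and its 95% CI". For the proportion, "the denominator to calculate the proportion will be the number of patients who took at least one dose during each time category". For the rate, "the denominator to calculate the incidence will be the duration of exposure in each time category". Up to week 60 there are four bands of 15 weeks.

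The same denominators are set for all-causality events in 8.2.3.2 and for patients treated mainly at 10 mg BID in 8.2.3.3 (1). Part (2) of 8.2.3.3 carries them into the higher- versus lower-dose analysis by reference. The SOC/PT table under Details of adverse reactions in 8.2.3.1 uses the same dosed-in-band denominator and dates a repeated PT by its first onset. It reports proportions only, with no incidence.

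The purpose is stated in 8.2.3.3, where the tables serve "to investigate the temporal change in the risk of occurrence of each event". Section 8.1.4, the general method for incidence, ends the exposure of a patient with the event at its first observation: "the period from the start of treatment to the day the event was first observed". Section 8.1.5 describes Kaplan-Meier plots, and 8.2.3.3 lists them for the dose subgroups.

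**The concern.** Numerator and denominator do not describe the same patients. A patient whose first herpes zoster occurs in week 5 and who continues treatment counts once, in the first band. That patient then sits in the denominators of the next three bands with no chance of being counted there. A later-band proportion is therefore an average over people at risk and people who are not.

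What is at stake is how the tables are read. If some of a fall across bands comes from the denominator, a reader may conclude that risk declines with time on drug. The share of patients no longer at risk also grows faster where events are more frequent, so a real difference between dose groups can look smaller in the later bands.

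**Working it through.** The documents give no expected band proportions, so there is no planned figure to reproduce. The check asks what the rule returns when the true risk does not change.

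**Inputs**
- Bands (SAP 8.2.3.1): "Time to onset [≤15 weeks, >15 to ≤30 weeks, >30 to ≤45 weeks, >45 to ≤60 weeks". Each lasts 15 × 7 / 365.25 = 0.2875 years.
- Event rate (Protocol 7.5.2): "the true incidence of herpes zoster in Japanese patients with ulcerative colitis is 8/100 person-years". Rates of 20, 40 and 50 per 100 person-years are assumptions, standing in for commoner elements such as the cytopenia, transaminase and lipid groups.
- Size (Protocol 7.5.1): "470 to be collected in the safety analysis set".
- Discontinuation pattern and the share of patients with the event who stay on drug: not given, so assumed.

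**Step 1: no discontinuation, all patients with the event stay on drug.** With S(t) = exp(−ht) and a band from t0 to t1:
- SAP proportion = S(t0) − S(t1)
- at-risk proportion = 1 − S(t1)/S(t0)
- SAP / at-risk = S(t0)

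For the last band, S(t0) = S(45 weeks), and 45 weeks = 0.8624 years.

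| Rate per 100 PY | At-risk proportion, every band | SAP proportion, >45 to ≤60 weeks | Ratio |
|---|---|---|---|
| 8 (documented) | 2.27% | 2.12% | 0.933 |
| 20 (assumed) | 5.59% | 4.70% | 0.842 |
| 40 (assumed) | 10.86% | 7.69% | 0.708 |

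At 8 per 100 the SAP proportions run 2.27, 2.22, 2.17 and 2.12% over the four bands. With 470 patients, the last band has about 470 × 0.0212 = 10.0 first onsets, divided by 470 rather than by the 470 × 0.933 = 439 at risk.

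**Step 2: some patients with the event stop.** If a share k of them is still dosed, the last-band ratio is S / [S + k(1 − S)]. At 8 per 100 this is 0.93 for k = 1, 0.9333 / (0.9333 + 0.0333) = 0.97 for k = 0.5, and 1.00 for k = 0.

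**Step 3: discontinuation for other reasons.** Assume 30, 15, 8 and 5% stop in successive bands at a constant rate within each band, and that having the event does not itself lead to stopping. A patient who stops early in a band counts fully in its denominator but contributes little time, so proportions fall where most stopping occurs.

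| Rate per 100 PY | SAP denominator, bands 1–4 | Event-free denominator, bands 1–4 |
|---|---|---|
| 8 | 1.91, 2.05, 2.08, 2.07% | 1.91, 2.10, 2.18, 2.22% |
| 50 (assumed) | 11.31, 10.73, 9.65, 8.49% | 11.31, 12.38, 12.86, 13.06% |

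Under the same constant hazard, the SAP proportion rises at 8 per 100 (last/first 1.08) and falls at 50 (0.75). The event-free denominator removes the fall but still rises, because it does not account for partial exposure.

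**Step 4: incidence.** With exposure stopped at first onset, the band incidence is flat at 8.0 per 100 person-years in Steps 1 to 3. If time after the event were included, the Step 1 setting would give 7.91, 7.73, 7.55 and 7.38.

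**Step 5: dose groups.** With assumed constant rates of 40 and 20 per 100 and Step 1 conditions, the last-band ratio of proportions is 10.86/5.59 = 1.94 among patients at risk, but 7.69/4.70 = 1.64 under the SAP rule. With 8 against 4 per 100 the ratio moves by only about 3% (0.933/0.966 = 0.966).

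**The case against.** The strongest reply is that the sound measures are already planned. In the safety-specification tables, the incidence with its 95% CI stands beside every proportion. Section 8.1.4 is the general method for incidence, and nothing in the band tables disapplies it. For the dose groups, where the SAP states the time-trend purpose, Kaplan-Meier plots are also listed. The tables are descriptive and no decision rule hangs on them. At the one documented rate the worst case is 0.15 percentage points on about 10 events, against an exact 95% CI for 10/470 of about 1.0% to 3.9%.

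Most of this stands, and it limits the point to the proportions. A reader might infer that the band incidence ignores the stop-at-first-event rule. The text does not show that: the band sentence lacks a cross-reference to 8.1.4, and the natural reading is 8.1.4 exposure divided among the bands. A reader might also take the time-trend purpose to be stated for all these tables. It is stated only in 8.2.3.3, for the dose groups, with the whole safety analysis set as comparator in part (1).

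The reply does not clear the proportions. The SOC/PT time-to-onset table has no incidence beside it, and 8.2.3.2 lists no Kaplan-Meier plot for all-causality events, although 8.1.5 describes the method in general terms. Where a sound measure is printed next to a distorted one, the SAP does not say which should carry a statement about change over time.

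**Conclusion.** The denominator rule is stated plainly and does not match a first-onset numerator, so the by-band proportions are not measures of risk among patients at risk. The understatement in the last band is about 7% relative at 8 per 100 person-years, and 16% and 29% at 20 and 40. These figures require a constant hazard, no discontinuation and every patient with the event staying on drug; only the first rate is in the documents.

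It is tempting to conclude that the rule always makes a constant risk appear to fall. The documents do not support that. Data collection ends at discontinuation, and 8.2.3.3 itself expects patients to stop during induction. If patients with the event stop, the effect disappears, and front-loaded stopping can turn the trend upward. What holds is that the apparent trend, and the later-band dose comparison, depend on event frequency and stopping pattern as well as on risk. The point is moderate for the safety-specification tables and matters most for the SOC/PT time-to-onset table.

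**What to change.** In SAP 8.2.3.1 (both the safety-specification timing table and the SOC/PT time-to-onset table), 8.2.3.2 and 8.2.3.3:

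1. Define the denominator of the band proportion as patients on treatment and free of that event or element at the start of the band.
2. State that band exposure for the incidence stops at first onset, with a reference to 8.1.4.
3. State that conclusions on change in risk over time, overall or by dose group, rest on that incidence or on Kaplan-Meier estimates. Item 1 alone does not correct for partial exposure within a band. The SOC/PT table, which has no incidence, should therefore not carry such conclusions.

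The cost is a few SAP sentences and minor programming. No new data are needed, since onset dates and treatment dates are already collected.
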